Our secondary objective is to estimate the effect of ImCT compared to psychoeducation on 1) level of depression, mania and anxiety and 2) general functioning and level of hopelessness (secondary outcome variables), 3) number of relapses into mania or depression and 4) changes in imagery characteristics. We hypothesise that (2a) symptoms of depression, mania and anxiety decrease and (2b) general functioning increase and level of hopelessness decrease (secondary outcome variables) more strongly in BD patients receiving ImCT than psychoeducation at T2, T3 and T4. Additionally, the effects of both treatments separately are also compared to baseline period preceding both treatments. We also hypothesise that 3) number of relapses into mania or depression after the end of ImCT are lower in the ImCT condition during the follow up period (T4) than in the psychoeducation condition. Finally, we hypothesises that 4) imagery characteristics will change more and problematic imagery decreases in the BD patients receiving ImCT at T2, T3 and T4, compared to baseline.

Note that, our primary outcome variable, mood variability, is measured in two ways. First, at baseline (T0), pre-intervention (T1), T2, T3 and T4. Second, mood variability is measured daily, during the four weeks baseline, during the intervention, and during the follow-up period (in total 16 weeks post intervention), in both the ImCT and psychoeducation conditions. Further note that the secondary outcome variables (2a), level of depression, mania and anxiety, are measured weekly throughout the duration of the study in both conditions and the secondary outcome variables (2b) general functioning and level of hopelessness and (4) changes in imagery are only measured at T0, T1, T2, T3 and T4. All measures are administered using an online secure server called Research Manager.

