4.4 Sample size calculation

To estimate the sample size needed for the between group design of this study, we used the study's primary outcome variable, mood variability, which is measured using the Affect Lability Scale (ALS-18).

The primary outcome variable for the between subjects design of the study, is the ALS-18, which was used in the audit (Hales et al., 2018) and in the pilot study by Holmes (Holmes et al., 2016). The effect sizes they found using the ALS-18 were $d = 0.8$ and $d = 0.99$ (see Table 1 below). We expect similar effect sizes in our study, that is $d = 0.9$ (the mean of the prior mentioned studies). Studies on the effect of psychoeducation have shown only moderate effects on medication adherence, knowledge of bipolar disorder and attitudes, but no or limited effect on mood variability or relapse, ranging from no effect (Bond & Anderson, 2015; Kurdal, Tanriverdi, & Savas, 2014) to a minimal effect (maximum of $d = 0.3$, but only in patients with less than 7 episodes), (Gumus, Buzlu, & Cakir, 2015; Morriss et al., 2016). We therefore expect an effect size of $d = 0.6$ (i.e., $d = 0.9$ minus $d = 0.3$). Based on prior mentioned effects of the ALS-18 we calculated the sample size needed, to power this study at 80% to detect an effect size of Cohen's $d = 0.6$ using a significance level of .05 two tailed T-tests using G*power 3.1.9.3 The calculated sample size needed is 45 in each group. The study of Holmes et al. (2016) showed a drop out 1 out of 15. After consulting with the research group from the audit and pilot study we expect a similar drop out rate in the current study. We therefore need a sample size of 48 in each group, 96 in total.

Table 1: Mean (SD) ALS-18 scores before and after ImCT in the pilot study of (Holmes et al., 2016)

Pre-Treatment	End of Treatment	4 week FU	12 week FU	24 week FU	Time	Pairwise differences, Bonferroni corrected pairwise t-test
46.36 (11.26)	35.54 (10.49)	35.43 (10.92)	36.36 (12.58)	34.71 (12.74)	F(4.48)= 6.75, $p < .001$	Pre vs 4w $t(12) = 3.77$, $p = .027$, $d = 0.99$; pre vs 12w

						$t(12)=3.58, p=.038, d = .84$; pre vs 24w $t(12)=4.62, p =.006, d = 0.97$
--	--	--	--	--	--	--

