8. STATISTICAL ANALYSIS

First, descriptive analyses will be used to establish mean scores, standard deviations and to identify outliers. Missing data from our primary outcome variable, will be listwise deleted. In our other outcome variables, data will only be included if pre- and post-measures are completed.

Second, the data will be checked with respect to violation of assumptions (such as error independency, non-normal distributions) for variance-based models.

Primary outcome variable: mood variability:

To assess if there is a stronger decrease in mood variability in the ImCT intervention condition as compared to the psychoeducation condition, multivariate repeated measures analyses are applied. Dependent variables are the scores on the ALS-18 (baseline, T0; pre-treatment, T1; post-treatment, T2; 8-weeks follow-up, T3; 16-weeks follow-up, T4) with treatment condition (ImCT, psychoeducation) as between subjects variable.

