To assess if (2a) level of depression, mania and anxiety, (2b) general functioning and coping, and hopelessness increase/decline more in the ImCT intervention compared to psychoeducation treatment two types of multivariate repeated measures analyses are applied, both with treatment condition (ImCT, psychoeducation treatment) as independent, between groups variable. In the first type of analyses, the dependent variables are the scores of the weekly measures for depression, anxiety and mania (QIDS-SR, BAI, ASRM). In the second type of analyses, time (T0, T1, T2, T3 and T4) is used as within between subject variables and scores of the same instruments and general functioning and coping and hopelessness (ALS-18, IFE-RIFT, BHS) are used as dependent variables.

To assess if (3) number of relapse into mania or depression decline more in the ImCT intervention compared to psychoeducation treatment Chi-square analyses are applied with as dependent variable number of relapses into mania or depression, using cut-of scores on the ASRM and QIDS-SR during the follow-up period and treatment condition (ImCT, psychoeducation treatment) as between groups variable.

To assess if (4) problematic imagery decreases and imagery characteristics changes more by using the ImCT intervention compared to psychoeducation treatment, comparable to 2a and 2b, two types of multivariate repeated measures analyses are applied, both with treatment condition (ImCT, psychoeducation treatment) as between groups variable. In the first type of analyses, the dependent variables are the scores of the weekly measures of imagery (VAS). In the second type of analyses, time (T0, T1, T2, T3 and T4) is used as within between subject variables and scores of imagery (MICQ-BD and DIS) are used as dependent variables.

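### The secondary T0–T4 analysis lists the primary outcome (ALS-18) among its dependent variables, so a primary effect alone can make a secondary omnibus test significant

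*Combined protocol and SAP*

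**What the plan says.** Section 2 expects secondary benefits in symptoms (2a) and in functioning and hopelessness (2b), "more strongly in BD patients receiving ImCT than psychoeducation at T2, T3 and T4". On the schedule it says that "level of depression, mania and anxiety, are measured weekly throughout the duration of the study in both conditions", whereas "general functioning and level of hopelessness and (4) changes in imagery are only measured at T0, T1, T2, T3 and T4". Section 6.1.2 assigns the QIDS-SR, ASRM and BAI to the 2a constructs, and the LIFE-RIFT and BHS to the 2b constructs.

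The ALS-18 has a different role. Section 4.4 states: "The primary outcome variable for the between subjects design of the study, is the ALS-18". Section 8 gives it a separate repeated-measures analysis over T0–T4 with treatment arm as the between-subjects factor: "Dependent variables are the scores on the ALS-18".

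For 2a and 2b, Section 8 then plans two types of analysis. In the first, "the dependent variables are the scores of the weekly measures for depression, anxiety and mania (QIDS-SR, BAI, ASRM"). The second is introduced by "In the second type of analyses, time (T0, T1, T2, T3 and T4) is used as within between subject variables", and continues: "scores of the same instruments and general functioning and coping and hopelessness (ALS-18, IFE-RIFT, BHS) are used as dependent variables". (IFE-RIFT is evidently the LIFE-RIFT.)

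The closing part of Section 8 says that between-group differences are analysed multivariately where possible, that post hoc tests (mostly independent t-tests) follow only a significant omnibus effect, and that a Bonferroni correction is applied.

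**The concern.** The sentence defining the secondary T0–T4 analysis has two faults.

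First, it includes the primary outcome. Under a joint multivariate test, a treatment effect confined to affect lability can produce a significant result for a set of scales presented as symptoms, functioning and hopelessness. That result would restate the primary finding, and it would open the way to post hoc tests on scales with no effect of their own.

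Second, the bracket does not match the text it follows. The words bring in three symptom scales by reference and add functioning and hopelessness, five scales in all. The bracket names three, one of which is none of those five. An analyst must decide whether the dependent variables are the bracketed three, the intended five, or all six. Left open, that choice could be made after the results are known.

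**Working it through.** **Step 1. The plan's own figure.** Section 4.4 uses d = 0.6, two-sided 5% and 80% power. A two-sample t-test needs 44.59, so 45 per group, with power 0.804 at 45. The stated 45 reproduces, and I use d = 0.6 and n = 45 per arm below.

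**Step 2. Which scale measures what.**

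| Scale | Construct (6.1.1, 6.1.2) | Schedule | Reached by 'the same instruments'? | In the bracket? |
|---|---|---|---|---|
| QIDS-SR | depression (2a) | weekly | yes | no |
| ASRM | mania (2a) | weekly | yes | no |
| BAI | anxiety (2a) | weekly | yes | no |
| LIFE-RIFT | functioning (2b) | T0–T4 | no, but its construct is named | yes |
| BHS | hopelessness (2b) | T0–T4 | no, but its construct is named | yes |
| ALS-18 | mood variability (primary) | T0–T4 | no | yes |

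The ALS-18 is the only bracketed label with no counterpart in the words before the bracket.

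**Step 3. Effect on a joint omnibus test.** Take a between-arm Hotelling T² test on p scales at one time point, with unit variances and a common correlation r. Let the ALS-18 differ by d = 0.6 and every other scale by zero. Then:

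- noncentrality λ = (n/2) × d² × [R⁻¹]₁₁ = 22.5 × 0.36 × [R⁻¹]₁₁ = 8.1 × [R⁻¹]₁₁
- reference distribution F with p and 2n − p − 1 degrees of freedom, tested at 5%

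| p | r | [R⁻¹]₁₁ | λ | df | P(significant) |
|---|---|---|---|---|---|
| 3 | 0 | 1.00 | 8.10 | 3, 86 | 0.64 |
| 3 | 0.3 | 1.16 | 9.40 | 3, 86 | 0.71 |
| 3 | 0.5 | 1.50 | 12.15 | 3, 86 | 0.83 |
| 6 | 0 | 1.00 | 8.10 | 6, 83 | 0.50 |
| 6 | 0.3 | 1.26 | 10.18 | 6, 83 | 0.61 |
| 6 | 0.5 | 1.71 | 13.89 | 6, 83 | 0.77 |

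Three scales is the bracket taken alone. Six is the bracket plus the QIDS-SR, BAI and ASRM. With the ALS-18 removed, none of the remaining scales has an effect, and the joint test rejects at its nominal 5%. The correlations are my assumption, as the documents give none.

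**Step 4. Are 2a scores available at the T points?** From the durations in Section 3, T2, T3 and T4 fall at weeks 4 + 12 = 16, 16 + 8 = 24 and 16 + 16 = 32 for ImCT. For psychoeducation they fall at weeks 4 + 6 = 10, 10 + 8 = 18 and 10 + 16 = 26. Weekly QIDS-SR, ASRM and BAI scores are scheduled around each of these in both arms, so the data exist. The documents do not say which weekly score stands for each T assessment.

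**The case against.** The strongest reply is that this is one stray label in a secondary analysis of a feasibility study. The primary analysis, sample size and data collection are untouched. Section 8 does not say that the scales share one model. If each has its own, the ALS-18 cannot affect the LIFE-RIFT or BHS result, and the percentages above do not apply. Even under joint modelling, the planned follow-up is mostly t-tests with Bonferroni correction. A t-test takes one scale at a time, so scales with no effect should usually show none, and an omnibus result driven by the ALS-18 need not become a claim about functioning or hopelessness. The calculation is also simplified: it uses one time point instead of five, and assumes exactly zero effect on scales that correlate with an affected one.

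All of this limits the harm, and I accept it. It does not remove the fault. Section 8 prefers multivariate tests where possible, so joint modelling is a natural way to carry out the text, and the ALS-18 can then satisfy the condition for post hoc testing by itself.

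A reader might infer something stronger: that the ALS-18 has displaced the depression, mania and anxiety scales, so that hypothesis 2a is not tested at T2–T4. Looking only at the bracket makes this tempting, as does Section 6.1.2, which lists those scales as weekly measures only. The documents do not support it. The quoted sentence takes in 'the same instruments', and the only instruments named just before it are the QIDS-SR, BAI and ASRM. Those scales are also compared between arms in the weekly analysis, which runs through the same period.

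**Conclusion.** The point holds as a specification error of limited size. The ALS-18 is wrongly included in the secondary T0–T4 analysis, and the bracket conflicts with the sentence it sits in. If the scales are tested jointly, an effect on the ALS-18 alone makes the secondary omnibus test significant in about 64–83% of trials with three scales, or 50–77% with six, where 5% is intended. This rests on one time point, 45 per arm, d = 0.6 on the ALS-18, no effect elsewhere and assumed correlations of 0 to 0.5. If the scales are tested separately, what remains is a second run of the primary test under a secondary label. The conclusion does not extend to hypothesis 2a being untested at T2–T4. The primary analysis is unaffected.

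**What to change.** In the secondary-outcomes part of Section 8:

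- Delete the ALS-18 from the T0–T4 list and analyse it only as the primary outcome.
- For 2a at T0–T4, name the QIDS-SR, ASRM and BAI, and use the weekly score from the same week as each T assessment in the participant's own arm.
- For 2b, name the LIFE-RIFT and BHS only.
- State whether the scales within each set are modelled jointly or one at a time.

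In Section 6.1.2, add a sentence saying that the matching weekly questionnaire serves as the T0–T4 score for the QIDS-SR, ASRM and BAI, so that nothing is completed twice.

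The cost is a few sentences. No new data, visits or participants are needed.

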6. METHODS

6.1 Study parameters/endpoints

6.1.1 Main study parameter/endpoint

To assess the primary endpoint of this study (1), decrease of mood variability, mood variability is measured using the Affect Lability Score Short Version (ALS-18) (Oliver & Simons, 2004) at baseline (T0), pre- intervention (T1) and post intervention (T2), and at follow-up measurements at 8 (T3) and 16 weeks (T4) after treatment discontinuation in both the ImCT and psychoeducation conditions. The ALS-18 is a self-report scale measuring lability in affect and consists of 18 items. Ratings are made on a 4-point scale with a maximum score of 72. Scores range from A= very characteristic of me (4 points), to D= very uncharacteristic of me (1 point).

In addition we monitor changes in mood variability using the National Institute of Mental Health Life Chart Methodology (NIMH-LCM) Prospective Self-Rating (Denicoff et al., 2000). Participants rate their mood (both mania and depression) on a 9-point Likert scale, ranging from -4 (severe depression, admission required due to severe dysfunction) to 0 (stable mood) to +4 (severe mania, admission required due to severe dysfunction). Daily measurements are calculated during a 4-week baseline prior to start of either ImCT or psychoeducation, during the intervention and until follow up at 16 weeks. This method is advised given that traditional self-report mood ratings over a single time point are scarcely representative of mood variability in bipolar disorder.

6.1.2 Secondary study parameters/endpoints (if applicable):

The following parameters are used for the following secondary objectives:

To assess (2a) level of depression, mania and anxiety and (2b) general functioning and hopelessness (3) number of relapses into mania or depression decline/increase, we administer the following measures:

- Level of depression, using the Quick Inventory of Depressive Symptoms (QIDS-SR) (Rush et al., 2003). The QIDS-SR is a 16-item self-report rating scale in which the nine DSM 5 symptoms of major depression are incorporated. Answers are rated on a four-point Likert scale (0-3). The QIDS-SR is administered weekly throughout the duration of the study.

- Level of mania, using the Altman Self-Rating Mania Scale (ASRM-NL) (Altman, Hedekker, & Peterson, 1997). The ASRM-NL is a 5 item self-report instrument to measure severity of mania symptoms. This is administered weekly throughout the duration of the study.

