- Level of anxiety, using the Beck Anxiety Inventory (BAI) (Osman, Barrios, Aukes, Osman, & Markway, 1993). The BAI is a 21-item self-report questionnaire used for measuring the severity of anxiety. Answers are rated on a 4-point Likert scale (0-3). This is administered weekly throughout the duration of the study.
- Level of general functioning and coping: Participants rate their level of functioning using the Longitudinal Interval Follow up Evaluation – Range of Impaired Functioning Tool (Leon et al., 1999). This is a brief scale for people suffering from affective disorders, measuring four different functional areas (employment, interpersonal relations, satisfaction and recreation) on a 5-point Likert scale (low rating implies higher functioning). This is administered at T0, T1, T2, T3 and T4.
- Level of hopelessness: participants rate their hopelessness using the Beck Hopelessness Scale (Beck, Brown, & Steer, 1997), The BHS is a 20 item self-report scale measuring three aspects of hopelessness: feelings about the future, motivation and expectations. The BHS demonstrates good internal consistency (alpha = .93) and has high reliability in psychiatric samples (Beck et al., 1997). The BHS is administered at T0, T1, T2, T3 and T4.
- To assess number of relapses into mania and depression, scores on the above measures (ASRM for mania and QIDS-SR for depression) are used. Scores on the ASRM of 5 or more indicate a relapse into mania, a score of 10 or more on the QIDS a relapse into depression. This is measured using the weekly scores on the ASRM and QIDS-SR during the weekly measures in the follow up period (until 16 weeks after the end of either ImCT or psychoeducation).

To assess if (4) problematic imagery the following measures will be used:

- The Visual Analogue Scales of Imagery Characteristics (VAS-Imagery) have been tailored to BD populations. The scales range from 0-9. Examples are "How real / vivid / absorbing / preoccupying / compelling have your image(s) been over the past week"; "To which extent could you understand the role that the image(s) play in your mood instability?"; "To which extent could you find positive / helpful way of using the image(s)?" Target imagery is measured weekly throughout the duration of the study. Imagery characteristics are measured weekly throughout the duration of the study in both ImCT and psychoeducation treatment conditions.

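### The relapse aim is worded as a decline but defined and tested as a follow-up level; the chi-square is valid for hypothesis 3 but leaves out the weekly scores collected before allocation

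*Combined protocol and SAP*

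**What the plan says.** Two places word the relapse aim as a change. Section 6.1.2 introduces the secondary measures with "number of relapses into mania or depression decline/increase". Section 8 opens its relapse sentence with "number of relapse into mania or depression decline more in the ImCT intervention compared to psychoeducation treatment Chi-square analyses are applied".

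Three places define relapse as a level after treatment:

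- Section 2, hypothesis 3, expects that the "number of relapses into mania or depression after the end of ImCT are lower in the ImCT condition during the follow up period (T4").
- The scoring rule in section 6.1.2 says "Scores on the ASRM of 5 or more indicate a relapse into mania" and "a score of 10 or more on the QIDS a relapse into depression", and then "This is measured using the weekly scores on the ASRM and QIDS-SR during the weekly measures in the follow up period", up to 16 weeks after the intervention ends.
- The section 8 sentence itself goes on to set the dependent variable "using cut-of scores on the ASRM and QIDS-SR during the follow-up period", with treatment condition as the grouping variable.

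The scores needed for a baseline value already exist. Section 6.1.2 states "The QIDS-SR is administered weekly throughout the duration of the study" and says the same of the ASRM. Section 6.3.2 places four weeks of these measures before random allocation.

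**The concern.** An aim stated as a decline needs a value before treatment, and the planned test has none. A reader of section 8 cannot tell whether a non-significant chi-square means that relapse did not fall more with ImCT, or that it was not lower with ImCT.

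The second issue is precision. The scoring rule requires no earlier period below the cut-off. Among mood episodes, section 4.3 excludes only a current manic one. A patient who enters with a QIDS-SR of 10 or more can therefore stay there and be scored as relapsing into depression. Baseline score is then a plausible predictor of the outcome, and the relapse analysis does not use it. With about 45 patients per arm and a yes/no outcome, unused prognostic information may matter.

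**Working it through.** **1. The plan's own figure.** Section 4.4 gives 45 per group for d = 0.6, two-sided 0.05, 80% power. The noncentral t gives 44.59, so 45 (power 0.804). For dropout of 1 in 15, 45 × (1 + 1/15) = 48 as stated; 45 / (1 − 1/15) = 48.2 would round up to 49. The figure reproduces, but it concerns the ALS-18. No relapse rate or relapse power is given, so 45 per arm is the only input it supplies here.

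**2. What the chi-square responds to.** Suppose 24 of 45 patients relapse during follow-up in each arm. The two rows are identical, so chi-square = 0 and p = 1.00. Now vary an assumed baseline count:

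| Baseline, ImCT v psychoeducation | Decline, ImCT | Decline, psychoeducation | p |
|---|---|---|---|
| 24 v 24 | 0 | 0 | 1.00 |
| 36 v 24 | (36 − 24)/45 = 27 points | 0 | 1.00 |
| 24 v 36 | 0 | 27 points | 1.00 |

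The test does not change with the decline. This shows what the test measures; it is not a likely scenario. A baseline split of 36 v 24 gives z = 0.267 / √(0.667 × 0.333 × 2/45) = 0.267/0.099 = 2.68, p ≈ 0.007, which randomisation would seldom produce.

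**3. What the unadjusted test can detect.** Power = Φ[(|p1 − p2| − 1.96·SE0)/SE1], with SE0 from the pooled and SE1 from the separate proportions, n = 45 per arm. For 0.50 v 0.22, SE0 = √(2 × 0.36 × 0.64/45) = 0.101 and SE1 = √((0.25 + 0.172)/45) = 0.097. So (0.28 − 0.198)/0.097 = 0.84 and power is 80%. Across assumed control rates of 0.30 to 0.70, the difference needed for 80% power is about 23 to 29 points (0.30 v 0.07; 0.70 v 0.41).

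**4. What baseline adjustment adds (depression only).** All score parameters are assumptions.

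- Weekly QIDS-SR = stable patient effect + AR(1) residual; mean 6, total SD 4; shift of 0 or −2 in ImCT during follow-up.
- Baseline is weeks 1–4. Follow-up is weeks 17–32 in ImCT (4 + 12 weeks precede it) and weeks 11–26 in psychoeducation (4 + 6).
- Relapse is any follow-up week at 10 or more; 45 per arm; 1000 runs per setting.
- Uncorrected chi-square, against the likelihood-ratio test of arm in a logistic model with mean baseline QIDS-SR.

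| Between-patient share | Weekly autocorrelation | Chi-square power | Adjusted power | Gain (points) |
|---|---|---|---|---|
| 0.05 | 0.6 | 79% | 79% | 0 |
| 0.1 | 0.8 | 64% | 67% | 3 |
| 0.2 | 0.6 | 70.7% | 77.9% | 7.2 |
| 0.2 | 0.8 | 60.7% | 67.2% | 6.5 |
| 0.4 | 0.6 | 61.6% | 74.6% | 13.0 |
| 0.4 | 0.8 | 56.1% | 65.8% | 9.7 |
| 0.6 | 0.6 | 54.8% | 74.6% | 19.8 |
| 0.6 | 0.8 | 52.3% | 67.3% | 15.0 |

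An independent repeat of the six settings with share 0.2 to 0.6 gave 50–73% against 65–78%, a gain of 4 to 19 points. With no effect, the six settings gave rejection rates of 3.8–5.3% for the chi-square and 4.3–5.3% for the adjusted test. In those settings the correlation between mean baseline and mean follow-up QIDS-SR was 0.34 to 0.79. Neither the ASRM nor the medication stratum was simulated.

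**The case against.** The strongest reply is that only a verb is wrong. The hypothesis, the scoring rule and the section 8 dependent variable agree, and the wording in section 6.1.2 closes an introductory list covering several outcomes; it is not a scoring rule. Because baseline precedes allocation, being lower in follow-up and having declined more are, in expectation, the same treatment contrast. An unadjusted comparison of a secondary binary outcome is a legitimate choice in a trial that calls itself a feasibility study and was not sized on relapse. This largely stands. It is why the remedy for the wording is an edit and not a new endpoint.

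It is also fair that the power gain rests on assumed figures and can vanish, and that nothing is shown for mania. Current manic episodes are excluded at entry, so baseline ASRM may be restricted and predict less. That stands too.

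Two stronger readings should be resisted. A reader might infer that chance baseline imbalance makes the chi-square biased. The null rejection rates above are near 5%: imbalance is already covered by the error rate, and what is lost is precision. A reader might also infer that the baseline weekly scores go unused. They are left out of the relapse test only; section 8 analyses the weekly QIDS-SR and ASRM by repeated measures under aim 2a. The section 8 rule requiring pre- and post-measures decides who is included and does not bring baseline into the relapse test.

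The reply does not remove the mismatch in wording, nor the fact that a possible gain in precision is available from data already held.

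**Conclusion.** The point holds as a wording mismatch and a missed gain in precision on a secondary endpoint. It may be tempting to conclude that the plan has two rival definitions of relapse and that its test cannot answer its question. The documents do not support that: the section 8 sentence itself limits the outcome to follow-up, as hypothesis 3 and the scoring rule do. The chi-square is a valid test of hypothesis 3, provided the unit is the patient. *Number of relapses* leaves open whether patients, episodes or weeks are counted, and repeated weeks from one patient would not be independent.

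The gain from adjustment for depression relapse runs from about nil (between-patient share 0.05) to about 20 percentage points of power (share 0.6). This assumes a QIDS-SR mean of 6, SD 4, a 2-point effect, any-week relapse and 45 per arm. The direction is plausible because the cut-off rule does not require patients to start below it; the size is unknown until baseline data are seen. No size is claimed for mania.

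**What to change.** - In sections 6.1.2 and 8, replace the decline wording with *lower during follow-up*, to match hypothesis 3. A raw change in counts would not serve anyway, with 4 baseline weeks against 16 follow-up weeks.
- Define the outcome per patient: any follow-up week at or above the cut-off already stated, separately for depression and mania.
- Analyse each by logistic regression on arm, adjusted for the patient's mean QIDS-SR (depression) or mean ASRM (mania) over the four baseline weeks, and for the medication stratum used in randomisation (section 6.2).
- Report the marginal (standardised) risk difference with its 95% interval. Keep the chi-square as a supplementary table.

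The cost is a few sentences and one regression per outcome, with no new data, visits or patients. An adjusted model is less simple to read than a cross-table; the marginal risk difference largely answers that, and an effect with its interval is also more useful to the planned larger trial than a p-value.
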